1.2 Study Design

This is a 1:1 randomized, double blind, dummy controlled multicenter trial to evaluate the efficacy and safety of ThermoDox plus sRFA compared to sRFA alone using standardized treatment dwell time ≥ 45 min. for solitary HCC lesions ≥ 3.0 cm to ≤ 7.0 cm for 550 subjects at up to 100 study centers.

An sRFA treatment for this protocol is defined as the dwell time of ≥ 45 minutes measured from the first activation of the RFA probe to produce coagulative necrosis of target tissue through removal of the RFA probe

after the final ablation cycle or deployment. This includes the multiple ablation cycles and repositioning time between cycles for an individual subject.

Eligible HCC subjects will have a solitary lesion not amenable to curative resection consistent with clinical diagnosis of AASLD classification guidelines and will be candidates for RFA. Subjects will be randomly assigned to receive either standardized sRFA plus ThermoDox at 50 mg/m² or standardized sRFA plus a dummy infusion using a standardized RFA dwell time \geq 45 minutes. Randomization and analysis will be stratified by maximum lesion diameter (3-5 cm versus $>$ 5-7 cm) and RFA route (laparoscopic, open surgical, percutaneous).

Screening Period

Subjects will be evaluated up to 21 days prior to the RFA procedure date to establish eligibility for study treatment. Subjects must meet all the study inclusion/exclusion criteria prior to randomization to a treatment arm.

Treatment Period

Subjects who meet the eligibility criteria will be randomly assigned to either sRFA plus ThermoDox or sRFA plus dummy infusion using a web-based randomization system. The RFA procedure day will be Day 0 and subjects will return to the clinic Day 14 and Day 28. Subjects with a complete ablation by imaging will continue in the follow up period described below.

A subject who has an incomplete ablation is eligible for 1 retreatment procedure within 21 days after radiological imaging exam showing residual disease at Day 28. Subjects will be retreated only once with the same RFA equipment and treatment assigned at randomization. Baseline safety evaluations must meet the eligibility parameters prior to a retreatment. Subjects with a complete ablation after retreatment will be followed for both OS and PFS. If after 2 ablations the subject has local, distant intrahepatic, or extrahepatic HCC, then the subject will be considered a treatment failure and will have met the PFS endpoint. The subject is still followed for OS every 3 months after progression.

Among subjects who are not treatment failures, up to five repeat treatments are permitted to treat a recurrent lesion or to treat newly identified local or distant intrahepatic lesions at the Investigator's discretion after the PFS endpoint is reported and with agreement from the Sponsor. The subject must be eligible for retreatment consistent with the safety eligibility criteria and will be retreated with the same randomized treatment.

Subjects who develop extrahepatic lesions will have met the PFS endpoint and are no longer eligible for further protocol treatment; they will be followed for OS.

Follow up visits are performed Day 14 and Day 28 (+/- 3 days) following the treatment. Subjects with bilirubin levels $>$ 2.0 mg/dL and \leq 3.0 mg/dL will return to the clinic on Day 7 for additional safety assessments. Exclusion concomitant medications are to be restricted through Day 28 following study treatment.

Follow-Up Period

Following study treatment, subjects will undergo CT or MRI imaging scans (chest, abdomen, and pelvis) at months 1, 5, 9, 13, 17, 21, and 25 (+/- 2 weeks), then at 6-month intervals (+/- 2 weeks) until radiological progression is seen. The same imaging modality and measurement of assessment should be used to characterize disease at baseline and during follow up for an individual subject. Investigator determined radiological progression must be observed and recorded prior to beginning alternate treatments for HCC. Post-progression treatments will be reported and the subject will continue to be followed for OS.

To provide surveillance for any late hematologic, cardiac, or liver toxicity, the following additional safety assessments will be done:

- Physical examination, assessment of vital signs, ECGs, CBC with differential, serum chemistry, PT/INR and urinalysis at Month 5, Month 9, and Month 13 (+/- 2 weeks) or at disease progression, whichever occurs first.
- LVEF monitoring at Month 13 or at disease progression, whichever occurs first.
- Serum chemistry and PT/INR assessments at Month 17, Month 21, and Month 25 (+/- 2 weeks) or at disease progression, whichever occurs first.

The site will contact all subjects every 3 months after radiological progression to document vital status until the subject expires or withdraws consent from the study. The follow-up contacts across all clinical sites may be coordinated using the same 3-month interval.

1.3 Study Procedures and Timepoints

The study procedures and time points are described in Section 10 of the Protocol.

2. STUDY POPULATIONS

- Intent-to-Treat (ITT) population: This population includes all randomized subjects and is the primary population for subject characteristics and all efficacy parameters. All analyses using this population will be based on the treatment to which each subject was randomized.
- As-Treated (AT) population: This population includes all subjects who actually received at least one application of RFA plus ThermoDox (TR) or RFA + dummy infusion (PR). This population will be used for the safety analyses. All analyses using this population will be based on the treatment actually received.

3. DEFINITIONS AND DERIVED VARIABLES

Age (years): integer [(Date of Informed Consent – Date of Birth +1)/365.25]

Baseline results are those reported at the last visit on or before the Procedure Day 0 pre-dose visit.

Study Day: Date in question – Date of Randomization

Overall Survival is defined as the time (in months) from the date of randomization to the death date. In the absence of death confirmation or for subjects alive as of the OS cut-off date, survival time will be censored at the date of last study follow-up, or the cut-off date, whichever is earlier.

Progression-free survival is defined as the time (in months) from the date of randomization until the date of the Investigator-assessed radiological disease progression (PD) or death due to any cause. In the absence of PD confirmation or for subjects without PD as of the cut-off date, survival time will be censored at the date of last tumor follow-up.

Censoring Rules for the Secondary Efficacy Parameter: PFS

Description	Outcome	Date PD/Censored
No baseline radiological assessments	Censored	Randomization
Treatment failures (subjects with incomplete ablations after two RFA procedures)	PD event	Date of radiological assessment after 2 nd RFA procedure that shows residual disease
PD documented between scheduled visits	PD event	Date of earliest radiological assessment with evidence of PD
PD documented after one missed scheduled visit	PD event	Date of earliest radiological assessment with evidence of PD
Death before first radiological assessment	PD event	Date of death
Death between adequate assessment visits	PD event	Date of death
Death or PD after two or more missed scheduled visits	Censored	Date of latest radiological assessment prior to missing assessments
Alive with no PD at the analysis cut-off date	Censored	Date of last radiological assessment
Receive non-study cancer treatment before progression	Censored	Date of last radiological assessment before non-study cancer treatment initiated
Liver transplant or liver resection before PD	Censored	Date of last tumor assessment for progression before the procedure
Discontinues/Withdraws from study without progression; no other follow-up information	Censored	Date of last radiological assessment for progression before date of discontinuation

Treatment-emergent adverse events (TEAEs) are defined as those adverse events which start or worsen on or after the first dose.

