Target Lesion	Distant Intrahepatic Recurrence	Extrahepatic Disease	Overall Response
CR	No	No	CR
IR*	No	No	Treatment Failure
IR*	Yes	No	Progression
IR*	No	Yes	Progression
Local Recurrence	Yes or No	Yes or No	Progression
Any	Yes	Yes or No	Progression
Any	Yes or No	Yes	Progression

*After 2 RFA +/- ThermoDox treatment sessions within 21 days after Day 28 radiological examination.

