15.2.2 Secondary Endpoints

15.2.2.1 Progression-Free Survival (PFS)

Progression-free survival is defined as the time (in months) from the date of randomization until the date of the Investigator-assessed radiological disease progression or death due to any cause. Subjects who are alive with no disease progression as of the analysis cut-off date will be censored at the date of the last tumor assessment. Subjects who receive non-study cancer treatment before disease progression, or subjects with clinical but not radiologic evidence of progression will be censored at the date of the last evaluable tumor assessment before the non-study cancer treatment is initiated. If a subject undergoes a liver transplant or liver resection before progression is observed, then the PFS for this subject will be censored on the date of last assessment without documented progression prior to the procedure. Treatment failures (subjects with incomplete ablations after two RFA procedures) will be considered to have met the PFS endpoint and the date of the Day 28 assessment following the 2nd ablation procedure will be used as the progression date. Additional censoring rules details will be outlined in the SAP.

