6.3.3 Secondary Efficacy Variable(s)

PFS will be measured from the date of randomization to the first date on which one of the following occurs, as determined by CT or MRI scan:

- Death of any cause
- Treatment failure (inability to achieve Complete Response (CR) after two RFA \pm ThermoDox treatment sessions)
- Progression due to local tumor recurrence after initial CR

- Progression due to distant intrahepatic tumor recurrence
- Progression due to extrahepatic tumor recurrence

All secondary endpoints comparisons will be made at the 2-sided 0.05 significance level for the ITT population. Since PFS is the only secondary endpoint for regulatory registration purposes, no further multiplicity adjustments will be made. Assuming that OS demonstrates significance at the 1-sided 0.025 level, PFS can subsequently be tested at the 1-sided 0.025 level.

PFS will be analyzed with methodology applied to the OS endpoint. Specifically, PFS will be analyzed with the methodology specified in Section 6.3.1 and the supportive analyses in Section 6.3.2.

In line with FDA guidance (Clinical Trial Endpoints for the Approval of Cancer Drugs and Biologics, 2007), several sensitivity analyses for Progression-Free Survival are also conducted on the ITT Population as follows:

- Analysis that includes clinical progression as a PFS event in addition to the presence of radiological evidence of progression.
- Analysis including clinical progression as a PFS event that also counts initiation of non-study antitumor therapy as an event date rather than as date used to censor subsequent response assessments. (ITT population)
- An analysis that includes all death and response assessments (without censoring missed visits) and also counting as an event, clinical progression, the initiation of anti-tumor therapy or death through the date of cut-off for survival (ITT population)
- Analysis using the next scheduled visit as the event date for radiological progression when image assessment falls more than 1 month after a scheduled assessment. If reassignment of the progression date to the next scheduled visit results in a progression date after death, the death date is used as the event date. (ITT population)
- Kaplan-Meier curves of time to first, second, third, fourth and fifth radiological tumor assessments from date of randomization are done and compared between groups using the log-rank test. (ITT population)

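### Residual tumour at Day 28 with no second ablation meets no PFS event definition and can be censored at the scan that showed it

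*SAP*

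**What the plan says.** The PFS events are death, treatment failure, local recurrence, distant intrahepatic recurrence and extrahepatic recurrence (protocol 4.2.1 and 12.4.1; SAP 6.3.3).

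- **Treatment failure.** The SAP Section 3 row reads "Treatment failures (subjects with incomplete ablations after two RFA procedures" and is dated at the scan after the second procedure. Protocol 15.2.2.1 has the same two-procedure condition. In protocol Table 4 every incomplete-response row carries the footnote "After 2 RFA +/- ThermoDox treatment sessions within 21 days after Day 28 radiological examination".
- **Local recurrence.** SAP 6.3.3 words it as "Progression due to local tumor recurrence after initial CR". Protocol Table 3 likewise presumes a complete result at Day 28.
- **Second ablation.** Protocol 10.2 and 12.4 permit one but do not require it. It must fall within 21 days of the Day 28 scan, and safety criteria must be met. Protocol 8.5.4 takes subjects who miss the re-treatment criteria in that window off study.
- **Censoring.** SAP Section 3 censors non-study therapy at "Date of last radiological assessment before non-study cancer treatment initiated". It has similar rows for "Liver transplant or liver resection before PD" and "Discontinues/Withdraws from study without progression; no other follow-up information". Protocol 15.2.2.1 agrees: such a subject "will be censored at the date of the last evaluable tumor assessment before the non-study cancer treatment is initiated".

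PFS is the only secondary endpoint intended for registration. It is tested at one-sided 0.025 once OS succeeds (protocol 15.3.2.3; SAP 6.3.3).

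**The concern.** The plan foresees incomplete ablation and foresees that some of these subjects will not be re-ablated, yet gives that state no PFS outcome. The main analysis can then record a known local failure as progression-free up to the scan that showed the tumour. The same finding after a second attempt is an event.

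Whether the failure counts thus depends on access to re-ablation. That access depends partly on neutrophil and platelet recovery (protocol 8.5.4). One arm receives doxorubicin and the other a dummy infusion, so access could differ by arm and the censoring could be informative. What is at stake is the PFS hazard ratio and its test, and case-by-case classification of an outcome that could be fixed in advance.

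**Working it through.** **1. The plan's own figure.** The only event target is 197 deaths for OS. Schoenfeld's formula gives 4 × (1.960 + 0.842)² / (ln 0.67)² = 195.8, so 196 against 197. OS counts deaths only, so this point does not touch it. The documents give no PFS event count, PFS power or incomplete-ablation rate, so everything below on size is assumed.

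**2. The state against each event.** Take viable tumour at Day 28, one ablation, no new lesion, alive.
- Death, distant recurrence, extrahepatic recurrence: not met.
- Treatment failure: not met, because every version needs two procedures.
- Local recurrence: not met, because there was no initial complete response. One Table 3 criterion (growth of at least 10 mm from Day 28) might be applied later, but it sits under a definition that presumes complete treatment.
- Table 4: no row fits. The incomplete-response rows need two sessions, and the rows for any target-lesion status need a new lesion.

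**3. Where the subject goes.** A new lesion or death can still be an event if it comes first. Otherwise the censoring rows apply. If no scan came between, the censoring date is the Day 28 scan itself. Protocol 10.1.8 and 10.3 ask for later imaging, which would move the date but not create an event.

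**4. How many (assumed).** With 5–15% incomplete at Day 28 and 10–50% of those not re-ablated:
- low: 275 × 0.05 × 0.10 = 1.4 per arm
- high: 275 × 0.15 × 0.50 = 20.6 per arm

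**5. Direction, by hand.** Assume no drug effect, 27 incomplete responders per arm (about 10%), un-retreated 9 (ThermoDox) v 3 (control), and second-ablation success probability s. Then 18 v 24 are re-ablated. The excess of early events in the ThermoDox arm is:
- censoring rule: 18(1−s) − 24(1−s) = −6(1−s)
- event rule: [9 + 18(1−s)] − [3 + 24(1−s)] = +6s

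At s = 0.3, 0.5, 0.7 this is −4.2, −3.0, −1.8 under censoring and +1.8, +3.0, +4.2 under the event rule. The two rules err in opposite directions.

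**6. Size, by simulation.** Same set-up: 275 per arm, 36-month accrual, cut at 66 months (36 + 30), and no other dropout. A failed second ablation is an event at day 28 + 21 + 28 = 77. An un-retreated residual is censored or an event at month 1. The model is an unstratified Cox model with Breslow ties, with 3,000 trials per cell. Null PFS hazard ratio at an assumed 16-month median:

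| Un-retreated (ThermoDox v control) | Rule | s = 30% | 50% | 70% |
|---|---|---|---|---|
| 9 v 3 | censored | 0.986 | 0.989 | 0.992 |
| 9 v 3 | event | 1.011 | 1.018 | 1.018 |
| 3 v 9 | censored | 1.014 | 1.012 | 1.005 |
| 3 v 9 | event | 0.989 | 0.986 | 0.982 |

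Over medians of 12, 16 and 24 months the ranges were:
- 9 v 3: 0.979–0.994 (censored) and 1.007–1.023 (event)
- 3 v 9: 1.004–1.021 (censored) and 0.978–0.992 (event)
- equal counts: 1.00 under both rules

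Against the nominal 2.5%, the one-sided false-positive rate was 2.7–3.5% for censoring at 9 v 3 and 2.8–3.8% for the event rule at 3 v 9 (Monte Carlo error about 0.3 points). Only an extreme split does more: 19 v 3 gave 0.950–0.987 (censored) and 1.026–1.061 (event).

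**The case against.** **The event rule is not a cleaner main analysis.** This stands. In the table it is nearer 1.00 than censoring at 30% second-ablation success. Censoring is nearer at 70%, and is level or slightly nearer at 50%. If un-retreated subjects are instead a random sample of their arm, censoring is unbiased (0.997–1.003). The event rule's null rejection rate in that model is 4.0% at 3 v 9 and 10.8% at 3 v 19 (16-month median). A reader might infer that making these subjects events removes the bias; the calculations do not support that.

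**The censoring route is narrow.** This largely stands. Protocol 5.1, 10.1.8 and 12.4.1 want progression recorded before other HCC therapy, so the route is mainly the off-study path in 8.5.4 or withdrawal, after which Section 11 allows other therapy. Protocol 8.5.2 stops study treatment, not follow-up, so it does not itself censor anyone.

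**Residual after one attempt is not the same as residual after the final attempt.** This stands in part. Protocol 12.4.1 treats incomplete response as its own category, with one re-treatment allowed. That is a reason to choose the classification openly, not to leave it blank. PFS is investigator-assessed and a separate imaging manual exists. It may address this state, but it is not among the documents.

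**Existing analyses cover it.** This stands in part. One SAP 6.3.3 sensitivity analysis "counts initiation of non-study antitumor therapy as an event date rather than as date used to censor subsequent response assessments", and others count clinical progression. SAP 6.2.1 reports discontinuations with reasons, and 6.2.7 reports new therapy begun with no recorded progression. But those PFS analyses date the event at the therapy or clinical progression and leave the main result unchanged. A withdrawal with neither recorded stays censored. No table counts un-retreated incomplete responses.

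**Conclusion.** The gap is in the text and does not depend on any assumption: residual tumour at Day 28 with no second ablation has no PFS event rule, and its censoring date can be the scan that showed the tumour. Its size does rest on assumptions (27 incomplete responders per arm, 9 v 3 un-retreated, 30–70% second-ablation success, medians of 12–24 months). Under these the null hazard ratio moves by about 0.02 or less in either direction, and not at all when the counts are equal.

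A reader might infer that the rule favours ThermoDox, because myelosuppression could block re-ablation in that arm. The documents do not support a direction. They give no rate of incomplete ablation or of missed re-ablation, and protocol 3.3 describes the prior trial's neutropenia as reversible. Nor does the point reach the primary result: OS is unaffected, and PFS is tested only after OS succeeds. Severity is minor to moderate.

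**What to change.** Before unblinding:

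1. Add a row to the SAP Section 3 table for an incomplete response at Day 28 with no second ablation ever performed, giving one outcome and one date. Match it in protocol 12.4.1, Table 4 and 15.2.2.1. Any subject who has a second ablation, even a late one, stays under the existing two-procedure row. A condition tied to the 21-day window would make a late successful re-ablation a Day 28 event and give a late failed one two dates.
2. Run PFS both ways: as an event at the scan showing residual disease, and censored as now. Name in advance which is main and which is sensitivity.
3. Report by arm the number of un-retreated incomplete responses and the reasons, alongside the tables in SAP 6.2.1 and 6.2.7.

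This changes how outcomes are classified, not who is re-treated. The Day 28 scan is already collected. The cost is one SAP row, one further analysis, one table, and a protocol amendment with full review (protocol 18.1). If the event rule is made main, there will be more early PFS events. On nominal visit days an un-retreated residual could also be dated up to 77 − 28 = 49 days before a re-ablated failure, using knowledge that no second ablation followed.

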4. EFFICACY ENDPOINTS

Overall Survival is the primary efficacy endpoint of this study. All patients will be monitored for survival by recording their visits during routine follow up for response to treatment. The visits are scheduled to occur every four months from the first imaging study confirming complete ablation until month 25 or radiological progression, whichever comes first. If patients have not demonstrated radiological progression at month 25 then the imaging visit schedule is reduced to every six months until progression. Survival is confirmed at every imaging visit. Once radiological progression is confirmed then follow up for overall survival will be confirmed every three months. It is expected that subject follow up will be about five years.

Progression-free Survival is the secondary efficacy endpoint of this study. The protocol incorporates modified RECIST (mRECIST) developed for HCC clinical research as a basis to evaluate tumor response. CT or MRI scans (chest, abdomen, and pelvis) will be done at baseline and post-treatment at months 1 (Day 28), 5, 9, 13, 17, 21, 25, then every 6 months until radiological progression is seen.

5. SAFETY ENDPOINTS

- Adverse events
- Laboratory assessments: hematology including CBC with differential, clinical chemistry, PT/INR, and urinalysis
- Physical Examinations
- Vital signs
- 12-Lead Electrocardiograms (ECGs)
- Echocardiograms/MUGA scans
- LVEF monitoring

Adverse events (AEs) assessment will begin at time of signing informed consent through Day 28 visit following the last study treatment. Adverse events which are assessed as possibly, probably, or definitely related to study treatment will be recorded at any point during the trial and must be followed until resolution or the subject is clinically stable.

Other safety data including physical examinations, vital signs, 12-Lead ECGs, echocardiograms/MUGA scans, LVEF monitoring and hematology, clinical chemistry, and urinalysis will be assessed through Day 28 following study treatment.

To provide surveillance for any late hematologic, cardiac, or liver toxicity, the following additional safety assessments will be done:

- Physical examination, assessment of vital signs, ECGs, CBC with differential, serum chemistry, PT/INR and urinalysis at Month 5, Month 9, and Month 13 or at disease progression, whichever occurs first.
- LVEF monitoring at Month 13 or at disease progression, whichever occurs first
- Serum chemistry and PT/INR assessments at Month 17, Month 21, and Month 25 (+/- 2 weeks) or at disease progression, whichever occurs first.

Subjects with elevated bilirubin levels > 2.0 mg/dL and ≤ 3.0 mg/dL at baseline will return to the clinic on Day 7 for additional safety assessments.

6. STATISTICAL METHODOLOGY**6.1 Statistical and Analytical Issues****6.1.1 Statistical Methods**

Continuous variables will be described in terms of mean, standard deviation, median, minimum, and maximum for each treatment arm. Qualitative variables will be presented in terms of frequency and percent for each treatment arm.

In summary and analysis tables of continuous variables, the minimum and maximum statistics will be presented to the same number of decimal places as the original data. The mean, median, quartiles, and 2-sided 95% confidence interval (CI) will be presented to 1 more decimal place than the original data. The standard deviation and standard error will be presented to 2 more decimal places than the original data.

In summary tables of categorical variables, the number of non-missing observations and percentages will be presented. The denominator for each percentage will be the number of subjects within the population of the treatment arm (unless otherwise specified).

Baseline characteristics and the efficacy parameters will be summarized for the ITT population while the safety parameters will be summarized for the As-Treated population.

All statistical analyses will be performed using SAS® v9.4 or higher.

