10. SCHEDULE OF STUDY PROCEDURES

Table 1: Schedule of Study Evaluations

Protocol Section	Procedure/Test	Screening / Baseline	Treatment Period ¹							Follow-Up Period			
			Procedure Day			Post-Procedure Visits (+/- 3 days)				Safety and Efficacy Assessments			
		-21 Days	Pre-Dose	Time 0	RFA + 15 min.	Post RFA	Day 7 ²	Day 14	Day 28	M5, M9, M13 or Progression ³	M17, M21, M25	6 Month Interval after M25	3 Month Interval after Progression
Evaluation and Observations													
17.1	Informed Consent	X ⁴											
10.1.3	Demographics and Medical History	X											
10.1.5	Physical exam	X				X	X	X	X				
10.1.6	Vital Signs	X ⁵	X ⁵			X ⁵	X	X	X	X			
10.1.7	ECOG Performance	X											
14	Adverse Event Eval.	X	→	→	→	→	→	→	X ⁶	X ⁶			
11	Con. Med. Update	X	→	→	→	→	→	→	X				
Treatment Procedures													
8.1	IRT System/ Randomization	X ⁷											
8.2	Pre-Medication Regimen		X ⁸										
8.2	IV Study Drug Infusion			X ⁹									
8.3-8.4	RFA Procedure				X ¹⁰								

Protocol Section	Procedure/Test	Screening / Baseline	Treatment Period ¹							Follow-Up Period			
			Procedure Day				Post-Procedure Visits (+/- 3 days)			Safety and Efficacy Assessments			
		-21 Days	Pre-Dose	Time 0	RFA + 15 min.	Post RFA	Day 7 ²	Day 14	Day 28	M5, M9, M13 or Progression ³	M17, M21, M25	6 Month Interval after M25	3 Month Interval after Progression
Safety Procedures/Lab Tests													
10.1.10	LVEF Monitoring	X ¹¹							X ¹¹	X ¹¹			
10.1.9	12-Lead ECG	X				X			X	X			
10.1.11	Serum pregnancy test	X											
10.1.12	CBC with differential	X					X	X	X	X			
10.1.12	Serum chemistry ¹²	X					X	X	X	X	X		
10.1.12	PT/INR	X					X	X	X	X	X		
10.1.12	Urinalysis	X					X	X	X	X			
Disease Assessment													
10.1.4	Biopsy		X ¹³										
10.1.8	Imaging ¹⁴	X							X	X	X	X	
15.2.1	Overall Survival ¹⁵												X ¹⁵

- Retreatment** – Subjects are eligible for one retreatment no later than 21 days after the Day 28 imaging scan. The retreatment must be the same (sRFA + dummy or sRFA + ThermoDox) as initially administered.
- Day 7 Visit** – Only subjects with a total bilirubin > 2.0 but \leq 3.0 mg/dL must undergo the additional safety visit on Day 7 post-RFA.
- Time of Progression** – Month 13 visit assessments are required at time of disease progression, whichever occurs first within the first 13 months. No further assessments required after progression is recorded

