6.1.2.2 Missing Data

All analysis will be based on available data to summarize safety and efficacy results. However, a conservative approach to partial dates and missing adverse event's relationships will be as follows:

- For the OS analyses, if a subject's death month and year are provided but the day is missing, the day will be set to the first day of the month, unless other qualifying study data support survival until a later date in the same month. The same concept will be applied if only the year is known. For a completely missing date of death, the fatality will be imputed to have been occurred on the last available contact of the subject where we still know he/she was alive.
- Adverse events with partial dates with the same month and year as the Procedure Day 0 will be considered as treatment-emergent adverse events.
- If an adverse event's relationship is missing it will be assumed to be related.

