6.4.4 Vital Signs

Vital signs, (temperature (in Celsius), blood pressure, pulse rate, and respiration) will be collected at the screening visit, Day 0: pre-dose assessment the morning of the RFA procedure, post-RFA within 15 minutes after completion of study drug infusion, within 30 minutes and 1 hour after RFA procedure, then every 2 hours until the subject is stable or discharged, Day 7 for subjects with elevated bilirubin, Day 14, Day 28, Month 5, Month 9, Month 13 or disease progression, whichever occurs first.

Vital signs will be summarized at each visit by treatment arm for actual values and change from baseline. The last on-study value will also be presented (called 'End of Study'), with change from baseline.

6.4.5 12-Lead ECGs

12-Lead ECGs will be acquired at screening, post Day 0: post RFA, Day 28, Month 5, Month 9, and Month 13 or disease progression, whichever occurs first.

For all 12-lead ECG abnormal findings will be presented for the actual values and change from baseline by visit and treatment arm.

Frequency tables will be provided by visit for QTcB and QTcF for the following categories:

- QTc <= 450 ms
- 450 ms < QTc <= 480 ms

- $480 \text{ ms} < \text{QTc} \leq 500 \text{ ms}$
- $\text{QTc} > 500 \text{ ms}$

Frequency tables will be provided by visit for the changes from baseline of QTcB and QTcF for the following categories:

- QTc change from baseline $\leq 30 \text{ ms}$
- $30 \text{ ms} < \text{QTc change from baseline} \leq 60 \text{ ms}$
- QTc change from baseline $> 60 \text{ ms}$

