6.4.6 Echocardiograms/MUGA scans for LVEF monitoring

A baseline echocardiogram (ECHO) will be carried out at the screening visit. Measurements with a MUGA scan are allowed if an echocardiogram cannot be performed; however, the same modality used at baseline must be used on Day 28 and at Month 13 or at time progression of disease, whichever occurs first.

Counts and percentages of abnormal echocardiograms/MUGA scan will be summarized for each treatment arm at each visit.

LVEF monitoring will be assessed at screening, Day 0: post RFA, Day 28, Month 5, Month 9, and Month 13 or disease progression, whichever occurs first.

LVEF % will be summarized by treatment arm at each visit for actual values and change from baseline.

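### By-visit ECG and echo/MUGA percentages are divided by the whole As-Treated arm, which understates late ECG rates, and the SAP does not say where the progression assessment is tabulated

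*SAP*

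**What the plan says.** SAP 6.1.1 states one rule for categorical tables: "The denominator for each percentage will be the number of subjects within the population of the treatment arm (unless otherwise specified". The sentence before it says that "the number of non-missing observations and percentages will be presented", and the next paragraph says that "the safety parameters will be summarized for the As-Treated population".

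SAP 6.4.5: "Frequency tables will be provided by visit for QTcB and QTcF for the following categories". The categories of QTc change from baseline are tabulated in the same way. SAP 6.4.6: "Counts and percentages of abnormal echocardiograms/MUGA scan will be summarized for each treatment arm at each visit". Neither section names a different denominator. SAP 6.1.2.2 says "All analysis will be based on available data to summarize safety and efficacy results", but that sentence does not name one either.

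On the schedule, Protocol 10.1.9 and SAP 6.4.5 place the late ECGs at Months 5, 9 and 13 or at progression, whichever is first. Protocol 10.1.10 and Table 1 footnote 11 place the late LVEF scan at Month 13 or progression. Table 1 footnote 3 requires the Month 13 assessments at the time of progression if that comes first, and then adds: "No further assessments required after progression is recorded". Protocol 10.3 asks sites to attempt the Month 13 evaluations in subjects who discontinue within the first year.

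**The concern.** The late visits exist to detect late toxicity, cardiac toxicity included, of an anthracycline-based product. A by-visit percentage is normally read as the proportion abnormal among those examined. Under the SAP's rule it is that proportion multiplied by the fraction of the arm examined.

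Two things follow. The absolute late rate is too low, whatever the treatment effect. And if one arm stays progression-free longer, more of it is examined at a given scheduled visit, so equal risk prints as unequal percentages. PFS is the secondary efficacy endpoint, so a difference between arms is something the trial is set up to look for.

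ECG and echo/MUGA are more exposed than other safety data. SAP 6.4.2 gives laboratory data a highest-post-baseline shift and a worst grade, and SAP 6.4.4 gives vital signs an end-of-study value. SAP 6.4.5 and 6.4.6 describe by-visit output only.

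**Working it through.** The documents give no PFS rate and no cardiac event rate, so there is no planned figure to reproduce on this point. Everything below is an illustration.

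**Inputs**
- Arm size: 550 randomised 1:1 (SAP 6.1.4), so 550 / 2 = 275 per arm, used as a stand-in for the As-Treated number. It cancels out of the percentages.
- Assumed: exponential PFS with control median 12 months (range 9 to 24).
- Assumed: PFS hazard ratio 0.67 (range 0.67 to 1.0). The value 0.67 is the OS design ratio, borrowed here.
- Assumed: 10% abnormal among those examined, in both arms.

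**Formulas**
- Control fraction progression-free at month m: S(m) = 2^(−m/12). ThermoDox: S(m)^HR.
- Printed percentage = true rate × fraction of the arm examined.
- With the non-missing denominator, both arms print 10% at every visit.

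**Scheduled columns, progressed subjects absent (HR 0.67)**

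| Visit | Control examined | ThermoDox examined | Printed, control | Printed, ThermoDox | Ratio |
|---|---|---|---|---|---|
| Month 5 | 0.749 (206) | 0.824 (227) | 7.5% | 8.2% | 1.10 |
| Month 9 | 0.595 (164) | 0.706 (194) | 5.9% | 7.1% | 1.19 |
| Month 13 | 0.472 (130) | 0.605 (166) | 4.7% | 6.0% | 1.28 |

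Over control medians of 9 to 24 months, Month 9 prints 5.0% to 7.7% for control and 6.3% to 8.4% for ThermoDox at HR 0.67 (ratio 1.26 down to 1.09). At HR 0.8 the Month 9 ratio is 1.15 down to 1.05. At HR 1.0 it is 1.00, but both arms still print 5.0% to 7.7% instead of 10%. The ratio does not depend on the assumed true rate.

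**Where the progression assessment goes**

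The SAP does not say. With the same inputs (median 12, HR 0.67):
- Left out of the Month 13 column: 4.7% control, 6.0% ThermoDox.
- Pooled as Month 13 or progression: nearly every subject has one value, so about 10% in each arm. Deaths without a progression visit still dilute it, but little. Protocol 3.3 reports death before progression in 4.1% (27/660) of Child-Pugh A patients in the prior trial, and 10% × (1 − 0.041) = 9.6%.
- Own Progression column over the whole arm, through Month 13: 10% × (1 − 0.472) = 5.3% control; 10% × (1 − 0.605) = 4.0% ThermoDox. The direction reverses.
- Assigned to the nearest scheduled visit: Month 9 regains those found to have progressed at the Month 9 scan but still lacks those who had progressed by Month 5, so about 7.5% and 8.2%.

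The Month 9 ECG is understated under every placement, by an amount that varies. For the Month 13 ECG and the late echo, even the sign depends on the placement.

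**The case against.** The strongest reply is that cardiac assessment does not simply stop. A reader might infer from footnote 3 that the Month 13 ECG and echo are done only in progression-free subjects, so that the longer-PFS arm must look more toxic at Month 13. The documents do not support this. The same footnote brings the Month 13 assessments forward to progression, and several sections repeat it. Under the protocol's schedule, the late echo is planned for every subject who either progresses or reaches Month 13. Pooling the two is a natural reading, and it removes nearly all of the distortion. This stands: no fixed direction or size can be claimed for Month 13.

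The other replies reduce the harm without removing it:
- The non-missing count is to be shown, so a careful reader can recompute the rate. The printed percentage is still the wrong one.
- In the QTc tables an unexamined subject falls in no category, so the rows sum to less than 100% and the gap is visible. The abnormal echo/MUGA percentage gives no such signal.
- The continuous summary is unaffected: "LVEF % will be summarized by treatment arm at each visit for actual values and change from baseline". Clinically significant ECG changes judged related are recorded as adverse events after Day 28 (Protocol 10.1.9). Neither replaces the category tables.
- The rule allows exceptions, and the table list is a separate document (SAP 8) that may contain one. The SAP text should nevertheless settle the denominator.

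**Conclusion.** The point holds in limited form. As written, the by-visit ECG percentages at Months 5 and 9 are divided by subjects who are no longer due for assessment, so late rates are understated. The arms are also distorted unequally if PFS differs. In the illustration, a 10% rate prints as about 5.9% and 7.1% at Month 9. The understatement needs no PFS difference; the arm distortion is zero at a PFS hazard ratio of 1. All sizes rest on assumed PFS and event rates.

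For the Month 13 ECG and the late echo, the defect is the missing rule for the progression assessment. Depending on that rule, the table shows a distortion in one direction, almost none, or the reverse.

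Severity is minor. Only descriptive safety tables are affected. The primary OS analysis and the continuous LVEF summaries are untouched.

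**What to change.** In SAP 6.4.5 and 6.4.6:
1. State that by-visit percentages use As-Treated subjects with a non-missing result at that visit and, for change categories, at baseline as well. Print that number beside each percentage.
2. State which visit column holds the assessment made at progression.
3. Add a worst post-baseline category per subject for QTc and for echo/MUGA.
4. Keep the whole-arm denominator for per-subject incidence tables such as TEAEs.
5. Reconcile the LVEF visit list. SAP 6.4.6 includes Day 0 after RFA and Months 5 and 9. Protocol 10.1.10, Table 1 footnote 11 and the first paragraph of SAP 6.4.6 give only baseline, Day 28 and Month 13 or progression. A whole-arm percentage at a visit with no planned scan would have no meaning.

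The cost is a few SAP sentences and changes to table shells, with no new data. Late denominators become smaller, so those percentages are less precise. They also describe only the subjects still under assessment, which the worst-category table helps to offset.
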